4.3.5.3 Quality of life related exploratory endpoint analysis

- Mean change in EQ-5D-5L index value from baseline to average EQ-5D-5L index value of weeks 28-52 will be analyzed using MMRM with treatment, visit, treatment-by-visit interaction, and baseline covariates, including the baseline index value, baseline Hb, CV history, geographic region and dialysis duration, as fixed effects and subject as a random effect.
- Change in EQ-5D-5L index value from baseline at weeks 12, 28 and 52 will be analyzed using the same MMRM as specified in Section 4.3.4 for this variable.
- Shift tables of EQ-5D-5L levels 1-5 by dimension and treatment arm.
- Mean change in EQ-5D-5L VAS value from baseline to average EQ-5D-5L VAS value of weeks 28-52 will be analyzed using MMRM with treatment, visit, treatment-by-visit interaction, and baseline covariates, including the baseline VAS value, baseline Hb, CV history, geographic region and dialysis duration, as fixed effects and subject as a random effect.
- Change in EQ-5D-5L VAS value from baseline at weeks 12, 28 and 52 will be analyzed using the same MMRM as specified above for this variable.
- EQ index value and VAS mean values (+SD) and median values (+ 25th & 75th percentiles) at baseline and each visit per treatment arm.

4.3.5.4 Hospitalization related exploratory endpoint analysis

All endpoints in this subsection will use OT+7.

- Proportion of subjects with hospitalizations and number of days of hospitalizations per PEY will be reported descriptively.
- Number of days spent in ICU per PEY for each treatment arm will be reported descriptively.
- Proportion of subjects who are re-admitted to hospital within 30 days per patient-exposure year for each arm will be reported descriptively.
- Proportion of subjects who are re-admitted to hospital within 30 days due to heart failure preceding a hospitalization due to heart failure per PEY for each arm will be reported descriptively.
- Proportion of subjects by number of days spent in a Skilled Nursing Facility that follow hospitalizations per PEY will be reported descriptively.
- Proportion and number of days of hospitalization-free survival on treatment will be reported descriptively.
- Proportion and number of days of hospitalization-free, emergency room- free, and skilled nursing facility-free survival on treatment will be reported descriptively. Proportion of subjects with days spent in a Skilled Nursing Facility that follow hospitalization and number of days spent in a Skilled Nursing Facility that follow hospitalizations per PEY will be reported descriptively. The total number of days covering both hospitalizations and subsequent days in Skilled Nursing Facility will also be reported.

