5.3.2 Hospitalizations

Details on hospitalizations (including emergency room/skilled nursing facility use) will be collected at each study visit. Reason, admission, discharge dates and type and reason for hospitalization will be recorded in the eCRF. Details on hospitalizations will also be collected at

follow-up visits in patients who prematurely discontinued treatment (only if they have taken at least one dose of study drug), until the projected date of the EOS visit.

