2.1.3 Safety Analysis Set

All subjects who received at least one dose of randomized study drug will be included in the Safety Analysis Set. Throughout the safety results sections, erroneously treated subjects will be accounted for in the actual treatment group. If a subject has received both treatments, only the initial period will be utilized. Subjects will be censored at either, 7, 3 or 0 days after last intake of study drug. Consequently, there will be three versions of the Safety Analysis Set, and they will be referred to as On-treatment+7 (OT+7), OT+3 and OT+0 respectively.

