3.1.6.4 Hospitalization related exploratory variables

- Number of hospitalization(s) and number of days of hospitalizations per PEY.
- Number of days spent in Intensive Care Unit (ICU) per PEY.
- Proportion of subjects who are re-admitted to hospital within 30 days per PEY.

- Proportion of subjects who are re-admitted to hospital within 30 days due to heart failure per PEY following a preceding hospitalization due to heart failure.
- Proportion and number of on treatment days of hospitalization-free survival.
- Proportion and number of on treatment days of hospitalization-free, emergency room- free, and skilled nursing facility-free survival. Number of days spent in a Skilled Nursing Facility that follow hospitalizations per PEY, and the total number of days covering both hospitalizations and subsequent days in Skilled Nursing Facility.

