4.1.1 Censoring

For analyses based on OT+7, subjects will be censored at 7 days after last intake of study drug, or the EOS visit, whichever is earliest.

For analyses based on OT+3, subjects will be censored at 3 days after last intake of study drug, or the EOS visit, whichever is earliest.

For analyses based on OT+0, subjects will be censored at last intake of study drug, or the EOS visit, whichever is earliest.

For analyses based on the ITT analysis set and FAS, subjects will be censored at their individual EOS visit, regardless of if they have discontinued study drug or not. Complete endpoint information will be pursued with every effort for all subjects, unless they exercise their right to withdraw consent. Subjects who withdraw consent will be censored at date of withdrawal of consent, and subjects who are lost to follow up (LTFU) will be censored at last available contact.

Subjects who withdraw consent and for whom only vital status (known to be alive at study closure, or date of death) may be obtained from public records, the occurrence of all components of the primary endpoint cannot be assessed, and will thus be censored at date of consent withdrawn for all analyses. However, the determination of all-cause death will utilize all publicly known mortality data, even that extending beyond date of consent withdrawal. The vital status information will be included in the analysis of all-cause death as a single endpoint, and in sensitivity analysis and tabulations. Similarly, complete information on the endpoint may not be obtained for subjects who are LTFU. Any such subject will be censored in the analysis at the last contact where all elements of the endpoint were assessed. A subject

will not be recorded as LTFU until the end of the study, after every allowable effort to get in contact has been made. Hence, it is anticipated that the number of subjects LTFU will be limited.

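### The two 30-day readmission endpoints stop observing 7 days after the last dose, so most or all of the window is lost when study drug is permanently stopped around an admission

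*SAP*

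**What the plan says.** SAP 3.1.6.4 defines the all-cause variable: "Proportion of subjects who are re-admitted to hospital within 30 days per PEY". A companion variable covers heart-failure readmission after a heart-failure admission. Neither is limited to time on treatment. The hospitalization-free survival variables in the same list are explicitly restricted to on-treatment days.

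SAP 4.3.5 makes ITT the default for exploratory analyses unless stated otherwise. SAP 4.3.5.4 overrides this for hospitalization: "All endpoints in this subsection will use OT+7". The list under that sentence includes both readmission endpoints: "Proportion of subjects who are re-admitted to hospital within 30 days per patient-exposure year for each arm will be reported descriptively" and "Proportion of subjects who are re-admitted to hospital within 30 days due to heart failure".

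SAP 4.1.1 defines the cut: "For analyses based on OT+7, subjects will be censored at 7 days after last intake of study drug, or the EOS visit, whichever is earliest". SAP 2.1.3 describes the same family of sets: "Subjects will be censored at either, 7, 3 or 0 days after last intake of study drug".

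Data collection goes further than the analysis. Protocol 5.3.2 records hospitalizations at "follow-up visits in patients who prematurely discontinued treatment (only if they have taken at least one dose of study drug", up to the projected EOS visit. SAP 1.2 says that subjects who stop early are followed for hospitalizations to EOS on ITT principles. SAP 4.3.6 plans an ITT repeat for RBC transfusion but none for hospitalization. No section says what happens to an index admission whose 30-day window runs past the cut, or whether the 30 days start at admission or at discharge.

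**The concern.** A 30-day outcome is measured with follow-up that can end 7 days after the last dose. A patient who permanently stops drug around an admission stays in the analysis with that admission, but little or none of the period in which a readmission could be seen. With no rule for incomplete windows, such a patient is tabulated as not readmitted.

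Stopping and admission can share a cause: Protocol 3.9.2 lists adverse events among the reasons for permanent discontinuation. The patients with truncated windows may therefore be among the sicker ones, and the readmission figures would then understate what happened to them. What is at stake is how two descriptive rows can be read, not a confirmatory result.

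**Working it through.** The plan gives no rate, sample size or power for readmission, so there is no stated figure to reproduce.

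**Inputs**
- Readmission window: 30 days (SAP 3.1.6.4 and 4.3.5.4).
- Cut: last intake + 7 days, or EOS if earlier (SAP 4.1.1).
- Start of window: discharge. This is an assumption. If the 30 days run from admission, the same formula applies with L measured to admission.

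**Days observed.** Let L be the number of days from the last dose to discharge (negative if dosing continues after discharge). When EOS does not intervene:

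days seen = max(0, min(30, 7 − L))

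| Permanent last dose | Days seen | Share of window |
|---|---|---|
| 23 or more days after discharge | 30 | 100% |
| 14 days after | 21 | 70% |
| 7 days after | 14 | 47% |
| On discharge day | 7 | 23% |
| 3 days before | 4 | 13% |
| 5 days before | 2 | 7% |
| 7 or more days before | 0 | 0% |

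The window is complete only if dosing continues to at least day 23 after discharge (23 + 7 = 30). Followed to EOS instead, any discharge at least 30 days before EOS has all 30 days.

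**Share of 30-day readmissions still counted.** This depends on when readmissions occur, which the documents do not give. As assumptions, take either an even spread over 30 days, or an exponential decline with half-life h, for which the share counted is (1 − 2^(−c/h)) / (1 − 2^(−30/h)), with c the days seen.

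| Last dose | Even spread | h = 14 days | h = 7 days |
|---|---|---|---|
| Discharge day (c = 7) | 23.3% | 37.9% | 52.7% |
| 3 days before (c = 4) | 13.3% | 23.2% | 34.5% |
| 7 or more days before (c = 0) | 0% | 0% | 0% |

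**Effect on an arm's total.** Let s be the share of index admissions that coincide with a permanent stop (not in the documents) and f the share counted among them. With equal readmission risk in all patients:

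counted / true = 1 − s(1 − f)

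- s = 10%: 90.0% (f = 0), 92.3% (f = 7/30), 95.3% (f = 0.527).
- s = 30%: 70.0%, 77.0%, 85.8%.

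If patients who stop have a higher readmission risk than the others, the loss is larger.

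**Does the per-PEY denominator correct this?** For a stop on the discharge day, 30 − 7 = 23 window days are lost, which is 77% of the window. Those days change the exposure denominator by at most 23/365.25 = 0.063 years. Scaling to exposure adjusts for total time on drug, not for time at risk after a discharge.

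**The case against.** The strongest reply is that this is a deliberate on-treatment analysis. SAP 4.3.8 uses OT+7 for safety generally, SAP 6.1 says the sets were aligned with the pooled plan, and Protocol 8.3.3 says on-treatment analyses will be emphasized. Hospitalization is not among the protocol's objectives, and these results are descriptive and outside the testing sequence. Part of the signal appears elsewhere: hospitalization makes an adverse event serious, treatment-emergent SAEs are also presented on the ITT set, and heart failure requiring hospitalization is adjudicated and followed after drug is stopped.

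Much of this stands, and it keeps the point minor. It does not repair the endpoint. Selecting admissions that occur on drug is a reasonable target, but a 30-day outcome after such an admission still needs 30 days. The ITT table of treatment-emergent SAEs is of uncertain help, because SAP 4.3.8.1 does not count events starting more than 7 days after the last dose as treatment-emergent. The reach of the pooled analyses cannot be judged from these two documents.

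A reader might go further in three ways that the documents do not support:
- **That all readmissions after stopping are lost.** Readmissions within 7 days of the last dose are counted. Only a permanent stop matters: the cut runs from the last intake, so a patient who pauses and resumes is not cut at the pause. Protocol 3.9.3.4 encourages restarting.
- **That the skilled-nursing endpoints have the same fault.** They are counts of days per PEY with no 30-day window.
- **That the loss favours one arm.** One reason for permanent discontinuation, more than one cycle of erythropoietin-analogue rescue, applies to roxadustat only (Protocol 3.9.2). That pathway is triggered by low Hb and non-response, and nothing links it to stopping around admissions.

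**Conclusion.** The concern holds for the all-cause and heart-failure 30-day readmission endpoints. Measured from discharge, OT+7 leaves 7 of 30 days observed when the permanent last dose is on the discharge day, and none when it is 7 or more days earlier. Readmissions after the cut are missed although the plan collects them, and no listed sensitivity analysis recovers them.

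The overall size cannot be fixed from the documents. Under the assumptions shown, 90% to 95% of readmissions are counted if 10% of index admissions coincide with a permanent stop, and 70% to 86% if 30% do. The open-label design allows stopping to differ by arm, but the documents do not show that it does around admissions, so the direction of any between-arm difference is unknown. No confirmatory conclusion is affected, and this is a minor improvement to a descriptive table.

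**What to change.** In SAP 4.3.5.4, for the two readmission endpoints only:
- Select index admissions that start within OT+7.
- Count readmissions through 30 days after discharge, or to EOS if earlier, regardless of study drug status, and state that the 30 days start at discharge.
- Report the result as a proportion of subjects with an index discharge, alongside the planned OT+7 per-PEY figure. A separate denominator avoids dividing post-treatment events by on-treatment time.

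Leave the skilled-nursing and other hospitalization endpoints on OT+7. While the section is open, reconcile the order of events in the heart-failure item: SAP 3.1.6.4 has the readmission following the heart-failure admission, while the wording in 4.3.5.4 reverses it.

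The cost is SAP wording, one derivation and an added line for each endpoint. No new data collection is needed, though windows will remain incomplete for patients who withdraw consent, are lost to follow-up or are discharged less than 30 days before EOS. The downside is that a few post-treatment events enter a descriptive table, and they should be labelled as such.

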1.2 Study design

This is a Phase 3, multicenter, randomized, open-label, active-controlled study to evaluate the safety and efficacy of roxadustat compared to epoetin alfa for the treatment of anemia in dialysis subjects. Subjects on hemodialysis (HD) or peritoneal dialysis (PD) who have been treated with an erythropoietin analogue or have an indication for treatment with an erythropoietin analogue will be evaluated for eligibility and randomized at a 1:1 ratio to treatment with roxadustat (with discontinuation of prior erythropoietin analogue therapy) or to an active control group treated with epoetin alfa.

The study periods are as follows:

- **Screening Period:** Up to 6 weeks.
- **Treatment Period:** Subjects will be randomized (1:1) to open-label treatment with either roxadustat or epoetin alfa. Treatment duration is variable for individual subjects (estimated treatment up to 4 years). A common closeout will occur when the target number of MACE events has been accrued.
- **Post-Treatment Follow-Up Period:** 4 weeks from the end of treatment (EOT) visit to the end of study (EOS) visit. Subjects who discontinue study medication prematurely will be followed up for CV events, Hb measurements, vital status and hospitalizations until the end of the study (EOS), according to ITT principles, unless consent to participate is withdrawn.

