4.3.8.1 Adverse events

Adverse events will be coded using the Medical Dictionary for Regulatory Activities (MedDRA) version 20.0 higher.

An AE (classified by preferred term) started during the treatment period will be considered a treatment-emergent adverse event (TEAE) if it was not present prior to the first dose of study medication. An AE that starts more than 7 days after the last dose of study medication will not be counted as a TEAE.

The number, percentage and percentage per PEY of subjects reporting TEAEs in each treatment group will be tabulated by system organ class and preferred term; by system organ class; by preferred term and by system organ class, preferred term, and relationship to study medication. If more than one event occurs with the same preferred term for the same subject, the subject will be counted only once for that preferred term using the most severe and most related occurrence for the summarization by severity and by relationship to the study medication. In addition to reporting TEAEs by number of subjects, the table by system organ class and preferred term will also be reported by patient years and event rates. Thus, allowing for potential systematic differences in mean exposure between the treatment groups. The event rate for a particular AE will be derived as the number of subjects with the AE, divided by total number of days at risk for the AE across all subjects in given group, multiplied by 365.25 multiplied by 100.

The distribution of TEAEs by severity and relationship to study medication will be summarized by treatment group.

The incidence of common ($\geq 5\%$ of subjects in any treatment group) TEAEs, common treatment-emergent serious AEs (TESAE), and AEs leading to discontinuation of study medication will be summarized by preferred term and treatment group, sorted in decreasing overall (across treatments) frequency. Moreover, TEAEs leading to hospitalization by system organ class and preferred term will be presented. In addition, related deaths and fatal SAEs (i.e., events that caused death) will be summarized separately by treatment group, system organ class and preferred term. TEAEs with outcome of deaths and TESAEs will also be presented for the ITT analysis set.

TEAEs and TESAEs by system organ class and preferred term will also be reported with OT+3 and OT+0.

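### SAP 3.1.6.4 defines the number of hospitalizations per patient-exposure-year, but SAP 4.3.5.4 reports the proportion of subjects hospitalized, so the admission count is never produced and its replacement depends on time on drug.

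*SAP*

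**What the plan says.** The variable is defined in SAP 3.1.6.4: "Number of hospitalization(s) and number of days of hospitalizations per PEY". The planned analysis is the first bullet of SAP 4.3.5.4: "Proportion of subjects with hospitalizations and number of days of hospitalizations per PEY will be reported descriptively". The analysis set is fixed there too: "All endpoints in this subsection will use OT+7". Under SAP 4.1.1 this means that "subjects will be censored at 7 days after last intake of study drug, or the EOS visit, whichever is earliest". SAP 1.2 lets time on treatment vary by subject, with an estimate of up to 4 years.

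The remaining bullets of 4.3.5.4 cover intensive-care days, 30-day readmission (any cause and heart failure), skilled-nursing days, and hospitalization-free survival. None is a count of admissions.

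The heart-failure readmission measure is also worded differently in the two sections. SAP 3.1.6.4 has readmission "due to heart failure per PEY following a preceding hospitalization due to heart failure"; SAP 4.3.5.4 has subjects "re-admitted to hospital within 30 days due to heart failure preceding a hospitalization due to heart failure per PEY".

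**The concern.** An admission rate and a proportion of subjects ever admitted are different quantities. The rate counts every admission and divides by time at risk. The proportion counts a subject once and grows with the time that the subject is observed. A programmer working from section 4 would never produce the rate that section 3 promises.

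The substitution matters most when time on drug differs between arms, and the SAP treats that as a live possibility. For adverse events, SAP 4.3.8.1 adds exposure-based rates, "allowing for potential systematic differences in mean exposure between the treatment groups". For rescue treatments, which also recur, SAP 4.3.5.2 keeps a count per PEY. The trial is open-label, and Protocol 3.9.2 lists one reason for permanent discontinuation (more than one cycle of rescue with an erythropoietin analogue) that applies to the roxadustat arm only. Hospitalization has no such safeguard for its headline figure. At stake is a descriptive table that could make the arm with shorter exposure look better, or hide a difference in repeat admissions.

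**Working it through.** **Plan's own figure.** The documents state no admission rate, no exposure by arm and no expected proportion hospitalized, so there is nothing to reproduce. The SAP's power statement concerns hemoglobin and is not involved.

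**Step 1: the two sections side by side.**

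| Component | SAP 3.1.6.4 | SAP 4.3.5.4 |
|---|---|---|
| Days in hospital | per PEY | per PEY |
| Admissions | number, per PEY | absent; proportion of subjects instead |

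The change table in SAP 6.1 mentions no such switch, although it lists major changes only.

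**Step 2: crude proportion under equal true rates.** Assumptions: the same mean rate λ in both arms, 0.8 or 1.2 admissions per PEY, and mean exposure T of 1.6 or 1.8 against 2.0 years. Let admission risk vary between subjects as a gamma distribution with shape 1, all followed for T years. The proportion with at least one admission is then λT/(1+λT). The same formula holds if all subjects share λ and exposure is exponential with mean T.

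| λ | T = 1.6 | T = 1.8 | T = 2.0 | Gap, 1.6 vs 2.0 | Gap, 1.8 vs 2.0 |
|---|---|---|---|---|---|
| 0.8 | 1.28/2.28 = 56.1% | 1.44/2.44 = 59.0% | 1.60/2.60 = 61.5% | 5.4 points | 2.5 points |
| 1.2 | 1.92/2.92 = 65.8% | 2.16/3.16 = 68.4% | 2.40/3.40 = 70.6% | 4.8 points | 2.2 points |

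The arm with shorter exposure looks better although the rates are equal. Simulations with the same rates and gamma shape 1, under several distributions of exposure, gave gaps of 4.3 to 6.1 points at 1.6 against 2.0 years. At 1.8 against 2.0 years, with λ from 0.3 to 1.5 and either fixed or exponential exposure, the gap runs from 1.7 to 3.8 points. If T is the same in both arms, the gap is zero.

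The 4-to-6-point range presupposes variation between subjects. If every subject had the same rate and exactly the same exposure within an arm, the proportion would be 1 − exp(−λT). That gives 72.2% against 79.8% at λ = 0.8 (7.6 points) and 85.3% against 90.9% at λ = 1.2 (5.6 points).

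**Step 3: if PEY also divides the proportion.** Subjects hospitalized per PEY = λ/(1+λT).
- λ = 0.8: 0.8/2.28 = 0.351 against 0.8/2.60 = 0.308, ratio 1.14.
- λ = 1.2: 1.2/2.92 = 0.411 against 1.2/3.40 = 0.353, ratio 1.16.

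The shorter-exposure arm now looks worse, because exposure keeps accruing after the one admission that counts.

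**Step 4: the defined measure.** Admissions divided by PEY estimates λ in each arm: 0.80 against 0.80, or 1.20 against 1.20. The ratio is 1.00 whatever the exposure.

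**Step 5: repeat admissions with equal exposure.** Assume that 50% are hospitalized in each arm over 2 years, with 1.5 against 2.5 admissions per hospitalized subject. The proportions are identical. Admissions per PEY are 0.5 × 1.5/2 = 0.375 and 0.5 × 2.5/2 = 0.625, a ratio of 1.67. This loss does not need unequal exposure.

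**The case against.** Four points can be made for the plan, and most of them limit the weight of the concern.

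- **Repeat stays are not wholly lost.** A reader might infer that they are. The documents do not support that. Days in hospital per PEY includes days from repeat stays and is the same in both sections. Readmission within 30 days is reported, and days of hospitalization-free survival fall with every stay. Only the admission count is missing.
- **No test is attached.** A reader might infer a false-positive finding. The endpoint is exploratory and reported descriptively, and SAP 4.2.2 says that analyses outside the confirmatory sequence are interpreted descriptively. No alpha is spent and no claim depends on it.
- **The size is assumed.** The documents do not show that exposure differs between arms or in which direction, so they do not show that either drug is favoured.
- **The heart-failure wording is a slip.** Read literally, 4.3.5.4 places the readmission before its index stay. A reader might infer that index and outcome have been reversed. But the bullet still speaks of subjects re-admitted, and a readmission must follow an earlier stay, so the only coherent reading is that of 3.1.6.4.

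All four stand. None of them supplies the missing count. Section 4 still does not yield the variable that section 3 defines, and the proportion depends on exposure whether or not it is divided by PEY.

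**Conclusion.** The mismatch is real and minor. Followed as written, SAP 4.3.5.4 gives days per PEY as defined but replaces the admission count with a proportion that ignores later admissions and moves with time on drug. The consequence is a potentially misleading descriptive contrast.

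Its size is illustrative and rests on assumed admission rates and assumed exposure by arm. Under equal true rates it is about 4 to 6 points at 1.6 against 2.0 years, given variation in risk or exposure between subjects, about 2 to 4 points at 1.8 against 2.0 years, and nil at equal exposure. The absence of the admission count holds whatever the exposure. No confirmatory conclusion of the trial is affected.

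**What to change.** In the first bullet of SAP 4.3.5.4, report the total number of hospitalizations divided by total PEY, by arm, on OT+7, and keep the number of days of hospitalization per PEY. The proportion of subjects hospitalized may remain as a separate supplementary line, not per PEY. A rate ratio from a negative binomial model with log exposure as offset is optional; the descriptive rate is enough to match section 3.

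As a wording correction, make the heart-failure readmission bullet say, as in 3.1.6.4, that the readmission follows a preceding heart-failure hospitalization, and keep its per-PEY denominator.

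The cost is a small SAP text change and one table line. Protocol 5.3.2 already has admission and discharge dates recorded in the eCRF, so no new data are needed.
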